This patient population is typically elderly and frail. It is at risk of adverse effects secondary to inadequate pain management such as delirium, prolonged admissions and poor functional outcomes [1, 4]. Appropriate pain management involves multimodal analgesia. This includes simple analgesia, opioid analgesia and regional anaesthesia (nerve blocks). There is high morbidity and mortality associated with opioid use in this vulnerable population [5-7]. A recent Cochrane review demonstrates that regional anaesthesia including femoral nerve block (FNB) and fascia iliaca compartment block (FICB) is indicated in the treatment of hip fractures. These regional nerve blocks provide reasonable analgesia, reduce opioid requirements and limit opioid-related harm [8].

Fractured neck of femur are predominantly intracapsular fractures. The greatest concentration of sensory nerve endings is found in the anterior hip capsule, which is, therefore, the target of nerve blockade [9-14]. Understanding of the innervation of the anterior hip capsule was updated in 2018 by Short et al and published *Regional Anaesthesia and Pain Medicine* [15]. This study confirmed that the existing understanding that anterior hip capsule is innervated by branches of the femoral nerve (FN), obturator nerve (ON) and accessory obturator nerve (AON) [9-15]. They found that the AON contributed in 54% of cases [15], which is greater than the previously demonstrated 8-29% [16]. The AON was found to arise directly from the lumbar plexus in all cases [15]. FN innervation of the anterior hip capsule involves high branches (above the inguinal ligament) in 92% of cases and exclusively high branches in 54% of cases [15]. ON innervation of the anterior hip capsule involves high branches in 62% of cases and exclusively high branches in 31% of cases [15].

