All patients presenting to Lismore Base Hospital with fractured neck of femur (#NOF) are placed on the NOF pathway. The pathway suggests that patients on the NOF pathway should receive regional anaesthesia (nerve block) within 30 minutes of arriving at the Emergency Department. The nerve block performed will be determined by the treating clinician.

Inclusion and Exclusion Criteria

Inclusion Criteria

1. Adult patients (>18 years) presenting to Lismore Base Hospital Emergency Department with radiologically confirmed #NOF. The neck of femur fractures include:
 - a. Sub-capital fracture
 - b. Surgical neck fracture
 - c. Intertrochanteric fracture
 - d. Peritrochanteric fracture
2. The patient receives a nerve block for their fractured neck of femur in the Lismore Base Hospital Emergency Department
3. The nerve block may occur before or after the radiological confirmation of diagnosis

Exclusion Criteria:

1. Regional anaesthesia not provided in the Lismore Base Hospital Emergency Department
2. Allergy to amide local anaesthetics
3. Infection of the skin overlying at the overlying the site of potential nerve block
4. The patient has already received a nerve block for this fracture prior to arrival in at Lismore Base Hospital
5. Other reason at the discretion of clinician/s
6. Femoral shaft fracture

Block Standardisation

As this is an observational study, intervention is not dictated by the study, but is at the discretion of the treating physician. However, there have been efforts to standardise aspects of the care provided to improve the validity of this observational data.

In accordance with usual standards of practice:

- All nerve blocks are to be performed with ultrasound guidance. Needle tip and infiltration should be directly visualised with ultrasound.
- All nerve blocks are to be performed with continuous cardiac monitoring and intravenous access.

Nerve Block Kit:

To encourage standardisation of nerve blocks within hour department a nerve block kit is already in use. It contains:

- 80 mm x 21 gauge Pajunk SonoSpot needle (or alternative needle stocked by the department)
- 0.9% sodium chloride - 1 x 10mL vial
- 20 mL luer lock syringe
- 3 mL luer lock syringe
- Drawing up needle
- 25 gauge 38 mm or 23 gauge 35mm needle for local infiltration
- Dressing kit
- Chlorhexidine 2% in 70% ethanol skin prep solution (30 mL)
- Sterile ultrasound probe cover and gel

Standard Order Set:

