Minimum Sample Size Calculation: Application of Student's t-Test.

Calculation assisted by using the Simple Sample Size Calculator (Android application). [Appendix 2]

- One-sided test to assess for non-inferiority
- Two sample
- Error 0.05
- Sample allocation ratio of 1:2
- Standard Deviation = 2.4
- $\mu_0 = 4$, $\mu_1 = 2.5$ (difference in pain score reduction of 1.5)
- Target (Actual) Power = 0.8000
- **Sample size = 74 (25+49)**

Duration of Data Collection

At our institution, we had 203 patients present with fractured neck of femur in 2018 and in the first 6 months of 2019 we have had 79. This is an average of 15.67 per month. Presuming this average continues and we achieve an enrolment rate of 80% and a PENG block delivered to one-third of these patients, we could expect to enrol sufficient patients in 6 months. To ensure significant power is achieved, we plan to enrol patients for a minimum of 6 and a maximum of 8 months.

Enrolment may be terminated early if we achieve a minimum enrolment of 125 patients and 41 PENG blocks. These numbers would allow for assessment of superiority (two-sided test) sensitive to a difference in pain score reduction of 1.3/10. [Appendix 3]

Secondary Outcomes

In an attempt to measure patient important outcomes, we will collect data on:

- Onset Time for analgesia (defined as the time until the first pain recorded pain score that is $\geq 1.5 / 10$ less than the pre-block pain score.
- Subjective observed patient comfort during nursing cares
- Patient preference where crossover occurs.
- Rates of block failure
- Block duration of analgesia

Subjective observed patient comfort during nursing cares:

Nursing staff caring for patients will be asked to comment on the patient's pain during standard nursing cares that require movement. These may include:

- Transfer to or from a bed
- Transfer on and off a bedpan
- Change of bedding or pad
- Other

At the time of nursing care, nurses are asked to rate the patient's analgesia as adequate or inadequate

Patient Preference where crossover occurs

- Some patients will have a repeat nerve block in the preoperative phase
- Of this population, some will receive a nerve block that is different to the block they received in ED. Hence they will have received cross over treatment and can act as their own control to compare two blocks.
- Investigators will identify these patients and they will be asked which block they found to provide more comfort.

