- ❑ Documentation on a paper form SPIED ED Data Form [Appendix 4] in the emergency department. This is additional to usual documentation and may be replaced by utilising Medical Surveys for data entry in the ED.
- ❑ Subjective Observed Patient Comfort During Nursing Score. May be completed in paper form [Appendix 7] or within Medical Surveys.

Data Governance

Data Storage:

The completed SPIED ED Data Form [Appendix 4] will be filed by clinicians in a folder within the Acute clinical area of the Emergency Department at Lismore Base Hospital. The SPIED ED Data Form will be the enrolment record.. Completed forms will be frequently collected by the investigators and stored securely with the ED Support Offices, which require swipe card access. This data will be stored for 5 years after the completion of data collection and then destroyed.

All other paper forms associated with the SPIED Study will form part of the patient's hospital record and will be treated accordingly.

Data Access:

- Investigators who are clinicians at Lismore Base Hospital have access to the patient's electronic medical records in the usual fashion as they would for day to day clinical work.
 - Investigators who access a patient's file for the purpose of data collection rather than clinical care, will create an electronic entry to document that they are accessing the file for the purposes of the SPIED study.
- In the event that any research funding is obtained, a research assistant may have access to Medical Surveys data and eMR as do the investigators.

Statistical Analysis

Primary Outcome:

Reduction in pain scores over the first 12 hours after nerve block. We will apply the following statistical tests:

- Student's t-test to compare the reduction in pain score of patients who receive a PENGGB compared to FNB and FICB
 - Subgroup analyses of the cognitively impaired and non-cognitively impaired population. These populations will have pain scored by the PAINAD and VAS respectively.
 - Subgroup analysis of FNB and FICB separately

Secondary Outcomes

- Onset of block. Defined as the time until the first pain score ≥ 1.5 less than the pre-block pain score.
 - T-test
- Subjective observed patient comfort during nursing cares
 - Chi Square test
- Patient Preference in the event of crossover
 - Chi Square test
- Rates of block failure. Defined as not achieving a reduction in pain score of $\geq 1.5 / 10$
 - Chi square test

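### Separate t-tests in the cognitively impaired and intact strata cannot show whether the block effect differs between them, and the protocol names no comparison between strata (minor)

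*Protocol*

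**What the plan says.** The Statistical Analysis section of the protocol opens its primary-outcome list as the tests that will be applied. It gives Student's t-test for the reduction in pain score, PENG against the femoral nerve (FNB) and fascia iliaca (FICB) blocks. Two lines are indented beneath that test:

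- "Subgroup analyses of the cognitively impaired and non-cognitively impaired population", followed by a sentence saying that the first group is scored on PAINAD and the second on VAS;
- "Subgroup analysis of FNB and FICB separately".

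No interaction or other between-stratum comparison is named, and no rule is given for reading the two stratum results together. The primary-outcome section adds that VAS is taken at rest and on movement, whereas PAINAD is one observed score.

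**The concern.** A test within each stratum asks whether PENG differs from the other blocks in that stratum. It does not ask whether the difference is larger in one stratum than in the other. When each stratum has only moderate power, a significant result in one and a non-significant result in the other is common even if the true effect is identical.

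A report could then say that PENG works only in patients who rate their own pain, or only in those who cannot. Here the strata also use different instruments, so a discordant pair could reflect chance, scale or cognition, and the planned tests cannot tell which.

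**Working it through.** **Inputs from the protocol.** The sample-size section gives "One-sided test to assess for non-inferiority", error 0.05, "Standard Deviation = 2.4", a "difference in pain score reduction of 1.5", a 1:2 ratio, "Target (Actual) Power = 0.8000" and 74 patients (25+49). Duration of Data Collection gives 15.67 patients a month, 80% enrolment, one-third PENG and at most 8 months: 15.67 × 0.8 × 8 = 100.3, or about 33+67. It also gives an early-termination size of 125 with 41 PENG (41+84) for a two-sided test of 1.3.

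**Assumptions.** The impaired share f is not in the protocol; 30-50% is assumed. SD 2.4 and a common true difference are applied to both strata, although the scales differ. Both block groups are split in the same proportion.

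**Step 1: reproduce the plan.** The noncentrality is 1.5 / (2.4 × √(1/25 + 1/49)) = 1.5 / 0.590 = 2.54 on 72 df. One-sided power is 0.81, against a stated 0.80. For 41+84 and 1.3 points two-sided, power is 0.805. Both planned sizes reproduce.

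**Step 2: power within strata.** Noncentral-t power, with both groups scaled by f or 1 − f. Example at 25+49, f = 0.3:

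- impaired, 7.5 v 14.7: SE = 2.4 × √(1/7.5 + 1/14.7) = 1.08, power 0.383;
- intact, 17.5 v 34.3: SE = 2.4 × √(1/17.5 + 1/34.3) = 0.705, power 0.675.

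**Step 3: chance that exactly one test is significant.** The strata are independent, so P = p₁(1 − p₂) + p₂(1 − p₁). In the example, 0.383 × 0.325 + 0.675 × 0.617 = 0.54.

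| Setting (same true effect in both strata) | f = 0.3 | f = 0.4 | f = 0.5 |
|---|---|---|---|
| 25+49, one-sided, 1.5: power impaired / intact | 0.38 / 0.67 | 0.47 / 0.62 | 0.55 / 0.55 |
| 25+49, one-sided, 1.5: exactly one significant | 0.54 | 0.51 | 0.50 |
| 33+67, two-sided, 1.5: exactly one significant | 0.56 | 0.51 | 0.50 |
| 41+84, two-sided, 1.3: exactly one significant | 0.55 | 0.51 | 0.50 |

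At 25+49 both tests are significant in only 26-30% of studies (0.383 × 0.675 = 0.26; 0.547² = 0.30). The one-sided 25+49 figures also apply to a true difference of zero tested against a non-inferiority margin of 1.5, because the noncentrality is the same.

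**Step 4: smaller true differences.** At 33+67, two-sided, a true difference of 0.75 gives powers 0.122 and 0.228 at f = 0.3, so 0.122 × 0.772 + 0.228 × 0.878 = 0.29. At 0.5 it is about 0.19. With no difference in a superiority test it is 2 × 0.05 × 0.95 = 0.095.

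**Step 5: what an interaction can deliver.** SE = 2.4 × √[(1/a + 1/b)(1/f + 1/(1 − f))], where a and b are the PENG and comparator group sizes; normal approximation, two-sided 0.05.

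| Size | SE, f = 0.3 to 0.5 | Power for a 1.5-point difference in effect | Difference detectable with 80% power |
|---|---|---|---|
| 25+49 | 1.29 to 1.18 | 21-25% | 3.6 to 3.3 |
| 33+67 | 1.11 to 1.02 | 27-31% | 3.1 to 2.9 |

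If the effect is the same in both strata, this test signals a difference in about 5% of studies.

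**The case against.** **The protocol is silent rather than wrong.** It plans no claim that the effect differs by cognition, and an analysis plan not shown may add an interaction. That limits the severity. What stands is that the protocol fixes t-tests as the method for these strata and says nothing to prevent the pair from being compared by their p-values.

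**Separate analysis is defensible because the instruments differ.** This is correct. Stratum and scale coincide completely, so a block-by-stratum interaction cannot distinguish a different block effect from a different scale. It supports separate estimates, but not a comparison of separate significance verdicts.

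**The 50% figure is conditional.** Also correct. It needs the planned difference (or true equality tested against the 1.5 margin); with smaller superiority effects, disagreement is rarer.

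The documents do not support three stronger readings:

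- *That the same fault affects "Subgroup analysis of FNB and FICB separately".* That line splits the comparator into PENG v FNB and PENG v FICB. These are treatment arms, so there is no block-by-subgroup interaction to test. Disagreement there is also less frequent: about 28% one-sided at 25+49, assuming comparators of equal size and effect.
- *That leaving out fracture location is an error.* The background says "Fractured neck of femur are predominantly intracapsular fractures" and puts the block target in the anterior capsule, while the inclusion criteria also admit "Intertrochanteric fracture" and the peritrochanteric type. A reader might infer that the rationale predicts a larger PENG advantage in intracapsular fractures and that the mechanism goes untested. The protocol makes no such prediction, and its aims do not include testing the mechanism. Subtype is collected, so the analysis remains open.
- *That an interaction test would settle the matter.* At 21-31% power it mostly would not.

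**Conclusion.** The point holds for the cognitive strata only, and is minor. At the planned effect, a split verdict between the two tests is the likeliest single outcome (about 50-56%) even when the effect is the same in both. Separate p-values are therefore no evidence that the effect differs.

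The size rests on the assumed 30-50% impaired share, a common SD of 2.4 on both scales and a true difference of 1.5. A share of 20% would give about 60% at 25+49. The sample size, the early-termination rule and the primary comparison do not depend on these subgroups.

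**What to change.** In Statistical Analysis, replace the cognition line with text to this effect:

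- the difference in pain-score reduction between PENG and FNB/FICB is reported with a 95% CI in each cognitive stratum, labelled VAS or PAINAD;
- consistency is assessed by one block-by-stratum interaction, reported with its CI;
- no subgroup conclusion is drawn from the separate p-values;
- the interaction cannot separate cognition from scale and is imprecise (SE about 1.2-1.3 at 25+49 and 1.0-1.1 at 33+67), so a non-significant result does not show that the effects are equal.

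Leave the FNB and FICB comparison as a comparator split, outside this rule. Fracture subtype may be added as an exploratory interaction because it is linked to the anatomical rationale; this is optional.

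The cost is a few lines of text and no new data. The downside is that the interaction will usually be inconclusive, which the text should say in advance.

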A standard order set [Appendix 1] has been built into FirstNet (the electronic medical record). This order set includes blood tests, radiography, referrals and analgesia. This “NOF order set” has been approved by the #NOF pathway working group and is available to all medical officers in the Emergency Department. The investigators will facilitate Medical Officers to add this order set to their ‘favourite’ orders.

Data To Be Collected

Regional Anaesthesia Provided

- Type of nerve block
- Content of nerve block
- Experience of practitioner

Patient Demographics

- # NOF Subtype
- Baseline characteristics: age, gender, comorbidities, social history, opioid use

Pain Scores

1. Visual Analogue Scale (VAS) [Appendix 6]
 - a. 100mm scale. Measured in 1mm increments. Converted to a score from zero to ten.
 - c. Measured at rest and on movement
2. Pain Assessment in Advanced Dementia (PAINAD) [Appendix 6]
 - a. Paper or electronic calculator
 - b. Scored zero to ten

Patients who are cognitively intact will have pain scores measured using the VAS, converted to score from zero to ten.

Patients who have a history of significant dementia or who clinically have significant cognitive impairment will have pain scored by a nurse or doctor using the pain assessment in advanced dementia (PAINAD) score, also zero to ten.

Subjective Observed Patient Comfort During Nursing Cares

- A binary measure of analgesia. Adequate or inadequate?

Opioid intake

- At baseline
- Pre-hospital
- In ED prior to regional analgesia
- After regional analgesia

Standard Documentation

Documentation that is recorded as a usual part of patient care

Nerve Block: Clinicians will be encouraged to document the placement of nerve block and its content in a standardised fashion within the patient's medical record, as is usual practice.

Pain Scores: Pain scores are recorded in the electronic medical record alongside vital signs. This is usual practice of nursing staff in the emergency department and on surgical wards. The utilisation of the VAS pain score is however, a departure from usual practice. Other pain scores such as the numerical pain scale and faces pain scale are previously / currently used by nursing staff at Lismore Base Hospital.

Analgesia Intake: Will be recorded in the electronic medical record. This is usual practice.

Additional Documentation

Documentation that is additional to usual practice, for the purpose of this study

Additional Paper Documentation:

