1. SPIED Study Emergency Department Data Form [Appendix 4]
 - a. Emergency Department staff may choose to use this form in place of Medical Surveys should they prefer, or if there are logistical challenges encountered with Medical Surveys
2. Limb Observation Chart: [Appendix 6]
 - a. It is standard practice on the surgical ward for nursing staff to complete limb observations every 1-2 hours on patients with #NOF and record these on a limb observation chart.
 - b. This chart has been modified for the SPIED study to also record pain scores
 - c. Also includes pain score calculators for the VAS and PAINAD
3. Subjective Observed Patient Comfort During Nursing Cares [Appendix 7]

Primary outcome = reduction of pain score

VAS pain scores will be recorded at rest and on movement. Movement is defined as attempted hip flexion to 15 degrees. PAINAD scores will be single measure based on nursing observation.

This score will be documented at the following times:

- Prior to placement of nerve block in the emergency department
- 15, 30, 60 minutes post placement of block
- With routine limb observations on the surgical inpatient ward, approximately hourly

Data will be collected for 12 hours post nerve block (or the next documented score after 12 hours) or until the patient is moved to the operating room, whichever is sooner.

Sample size and statistical power

The rationale for sample size calculations:

- A reduction in visual analogue pain score of 13 mm (1.3/10) was established as being clinically significant by Todd et al in 1996 [26].
- A clinically significant difference between two treatments that reduce pain scores by 1.3/10 has not been well defined
- Cooper et al used 1.5/10 difference in pain scores as a definition of clinically significant difference between blocks [27].
- Newman et al found a standard deviation in pain score reduction of 2.4 in patients receiving regional analgesia for #NOF in 2013 [28]. This figure was used by Cooper et al for their power calculation in 2018.
- Cooper et al found standard deviations of 2.2 and 2.4 respectively for the FNB and FICB [27].
- A retrospective study of patients that received regional anaesthesia for # NOF at LBH in the first 4 months of 2019 was performed by co-investigators of this study. This data included 40 patients that received regional anaesthesia in ED, 6 of whom received a PENG block. Pain score documentation was not sufficiently reliable to inform power calculations for this observational study.

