- Treatment in this phase of the patient's journey will be decided by the acute pain service or duty anaesthetist. The investigators will have no influence over which repeat block the patient receives.

Block failure

- Defined as maximum pain score improvement of less than 1.5 out of 10.

Duration of analgesia from nerve block

- End of block effect defined as an increase in pain score to ≤ 1.0 from pre-block pain score in a patient who had a reduction in pain score of > 1.5 at any time.

Opioid Requirement

- Opioid intake will be measured by analysis of the electronic medication chart from the insertion of block until 12 hours have passed, or the patient is checked in to the operating theatre, whichever occurs first.
- This information will be converted to milligrams of oral morphine using the Faculty of Pain Medicine Opioid Calculator

Adverse events

In an effort to detect the incidence of adverse events, the investigators will:

- Perform a keyword search of the “Continuous Doc” feature of the electronic record, after the patient is discharged from the hospital.
 - Keywords:
 - Delirium
 - Sedation
 - Constipation / Constipated
 - Aspiration
 - Naloxone
- Review the electronic medication chart for use of:
 - Naloxone
 - Antibiotics

Surgery Waiting Time:

Time to surgery will be defined as the time from Triage in the Emergency Department to the time of Check In at Operating Theatre for operative fixation.

Data collection on our cohort for the purposes of the primary outcome will cease at the time of check in to the operating theatre or at 12 hours after the insertion of nerve block, whichever is sooner.

Mean, median and longest wait times will be recorded. This information will inform future practice at our hospital.

Data Collection and Storage

Primary Data Recording Methods:

Were discussed above and are summarised here:

- ❑ Documentation in the electronic medical record record (PowerChart / FirstNet / SurgiNet) as is usual practice for all patients treated in the emergency department and those admitted to the hospital
- ❑ Documentation on the paper SPIED Limb Observation Chart [Appendix 6] which is usual practice for patients admitted to the inpatient orthopaedic and surgical ward with fractured neck of femur. The standard chart has been modified for the SPIED study to include pain scores and pain score calculators.

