- Duration of analgesia. End of block effect defined as an increase in pain on movement score to ≤ 1.0 from pre-block pain score for that patient, in a patient who had a reduction in pain score on movement > 1.5 at any time.
 - T-test

Ethical Considerations

There are several ethical considerations in the design and implementation of this study. Throughout the study design process, the authors have consulted with key members of staff within our health service:

- ❑ *Director of Research: [name]*
- ❑ *Orthopaedic Clinical Nurse Specialist: [name]*
- ❑ *Acute Pain Service Clinical Nurse Consultant: [name]*
- ❑ *Surgical Clinical Nurse Educator: [name]*
- ❑ *Geriatric Medicine CMO: [name]*
- ❑ *Department of Anaesthesia Orthopaedic Special Interest Group: [name]*
- ❑ *Department of Anaesthesia research interest group: [name], [name]*
- ❑ *Pain Specialist: [name]*
- ❑ *LBH Nursing Infection Control: [name]*
- ❑ *Rural Research Education Manager: [name]*
- ❑ *Department of Emergency Medicine: Consultant group*
- ❑ *Emergency Department Clinical Nurse Educator: [name]*
- ❑ *Emergency Department Nurse Unit Managers: [name], [name]*
- ❑ *Director of Emergency Medicine Training: [name]*
- ❑ *NOF pathway working group headed by [name]*

Research merit and integrity

Merits of this research:

- We believe the PENGGB to have a superior anatomic basis for efficacy compared to other nerve blocks for neck of femur fractures. Early experience utilising the PENG block is promising.
- Early adoption of the PENGGB which, to our knowledge, has not been studied outside of Toronto, nor within an Emergency Department would place our institution in a leading position in the emergency management of # NOF.
- The generation of evidence supporting this therapy's safety and efficacy would be expected to increase its uptake both within our institution and at other institutions. A positive study would be expected to encourage further investigation in the form of a randomised clinical trial
- Generation of evidence that the PENGGB is inferior to the standard of care would appropriately discourage clinicians from changing their practice.

Integrity:

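### The single unadjusted primary t-test combines self-reported VAS and observer-rated PAINAD reductions, so an imbalance in cognitive impairment between blocks could bias the comparison

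*Protocol*

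**What the plan says.** Under Data To Be Collected (Pain Scores), the instrument depends on cognition. "Patients who are cognitively intact will have pain scores measured using the VAS, converted to score from zero to ten". Patients with significant dementia or cognitive impairment are instead rated by a nurse or doctor on the PAINAD, which also runs from zero to ten.

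Under the primary outcome heading, the measuring conditions differ: "VAS pain scores will be recorded at rest and on movement", whereas "PAINAD scores will be single measure based on nursing observation". The schedule is common to both: before the block, at 15, 30 and 60 minutes, then about hourly on the ward.

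Under Study Design (Current Practice), the treating clinician decides which block is given.

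Under Statistical Analysis, the primary test is "Student's t-test to compare the reduction in pain score of patients who receive a PENGGB compared to FNB and FICB". Nested below it is "Subgroup analyses of the cognitively impaired and non-cognitively impaired population", with the note that "These populations will have pain scored by the PAINAD and VAS respectively". No stratification, adjustment or conversion between scales is attached to the primary test. The minimum sample size of 74 (25+49) uses one SD of 2.4 and one difference of 1.5.

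Block duration is defined twice. The description of secondary outcomes reads "End of block effect defined as an increase in pain score to" a threshold, with no mention of movement. The Statistical Analysis section uses the movement score and limits the endpoint to effect "in a patient who had a reduction in pain score on movement".

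**The concern.** A shared zero-to-ten range does not make two instruments interchangeable. One is self-report, the other is an observer's rating. One separates rest from movement, the other does not. The plan does not say whether the rest or the movement VAS score joins the single PAINAD score in the t-test.

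In a randomised trial the instrument mix would be balanced on average, and pooling would mainly cost precision. Here nothing in the design balances cognitive impairment across blocks. If impaired patients receive one block more often, and PAINAD reductions are typically smaller or larger than VAS reductions, the t-test reads part of that difference as an effect of the block. This could produce a false non-inferiority or superiority result, or hide a true one. The planned subgroups would show the pattern but would not correct the primary result.

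The duration endpoint has a related defect. Patients scored on the PAINAD can have a duration under one definition and not under the other.

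**Working it through.** **1. The plan's own figure.** Inputs from Minimum Sample Size Calculation: one-sided 0.05, power 0.80, SD 2.4, difference 1.5, ratio 1:2. By normal approximation the PENG group needs 1.5 × [2.4 × (1.645 + 0.842)/1.5]² = 23.7, so 24+48 = 72. At the stated 25+49, power is 0.815 (normal) or 0.809 (noncentral t). The stated 74 is confirmed and is not in question.

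**2. Is the primary test pooled?** The protocol does not use that word. It names one test on all patients and puts the PAINAD/VAS split only among the subgroup analyses, so pooling is the natural reading.

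**3. Bias formula.** Suppose the block has the same effect on both scales. Let p be the impaired share in each group and m the mean reduction on each scale. The pooled difference is then off by

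bias = (p in PENG − p in FNB/FICB) × (m on PAINAD − m on VAS).

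It is zero if either bracket is zero. Because the outcome is a reduction from each patient's own baseline, a constant level difference between the scales cancels. Only different responsiveness matters.

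**4. Illustration.** Assumed, because the documents give neither quantity: 40% against 25% impaired, and a gap of 1 to 2 points. Bias = 0.15 × 1 to 0.15 × 2 = 0.15 to 0.30 points, which is 10% to 20% of the 1.5 difference.

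Standard error at 25+49 = 2.4 × √(1/25 + 1/49) = 0.590. By normal approximation:

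| Bias | One-sided error if bias favours PENG: 1 − Φ(1.645 − bias/0.590) | Power if bias goes against PENG: Φ((1.5 − bias)/0.590 − 1.645) |
|---|---|---|
| 0 | 0.050 | 0.815 |
| 0.15 | 0.082 | 0.740 |
| 0.30 | 0.128 | 0.652 |

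For the larger target of 125 with 41 PENG blocks (two-sided, difference 1.3), the same biases move the error from 0.05 to 0.062 and 0.101, and power from 0.811 to 0.711 and 0.590.

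**5. Wider range.** Gaps of 0.5 to 2.0 points and imbalances of 10 to 30 percentage points give a bias of 0.05 to 0.60. At 25+49 the one-sided error runs from 0.059 to 0.265, and power from 0.792 down to 0.453.

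**6. Price of stratifying.** Using inverse-variance weights over the two instrument strata, with SD 2.4 in each, at 25+49:

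| Impaired share, PENG / FNB+FICB (assumed) | Power for 1.5 |
|---|---|
| 40% / 40% | 0.815 |
| 50% / 30% | 0.802 |
| 50% / 20% | 0.780 |

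Under assumed shares of 20-50% impaired per group, the subgroups alone have power of about 0.43-0.49 (PAINAD) and 0.60-0.64 (VAS).

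**7. Duration.** One definition needs only a pain score. The other needs a movement score, which PAINAD patients do not have. This conflict can be seen in the text and needs no assumption.

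**The case against.** The strongest reply is that both the imbalance and the gap are hypothetical. The protocol's comparison of the blocks turns on anatomy, technique and operator skill, not cognition, so imbalance is possible but not indicated. Using change from baseline removes constant differences between scales. In the illustration the bias is small beside a standard error of 0.59. The results by instrument are already planned. All of this stands, and it limits what can be said about size. It does not show that the primary test is protected: the subgroups do not correct it and are underpowered on their own.

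Four stronger readings are tempting, and the documents do not support them.

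- A reader might infer that the PAINAD is recorded on one occasion only. The common schedule shows that it is one score per time point, without a rest/movement split.
- A reader might infer that the 1.5 margin belongs to the VAS. The 1.3 figure is stated as a visual analogue result, but 1.5 comes from another cited trial whose instrument is not named.
- A reader might therefore restrict the margin to VAS on movement. That would cut power to 0.68 (18+34) or 0.61 (15+29) if 30% or 40% of patients use the PAINAD, and it would drop impaired patients from the main conclusion.
- A reader might infer that mixing the scales costs substantial power even without imbalance. With 40% on PAINAD, a 2-point gap gives SD √(2.4² + 0.4 × 0.6 × 2²) = 2.59 and power 0.754 against 0.809. A 1-point gap gives SD 2.45 and power 0.795. Both results assume that 2.4 is a within-scale SD, which the protocol does not show.

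A separate analysis plan might add adjustment. The protocol itself nevertheless names the unadjusted test, and the duration conflict lies within its own text.

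**Conclusion.** The concern holds as a vulnerability of the primary analysis, not as a demonstrated bias. As written, the plan lets an imbalance in cognitive impairment enter the block comparison through the choice of pain instrument.

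Confidence in the mechanism is high. Confidence in the size is low, because the illustrative 0.15 to 0.30 points, and the error and power figures that follow, rest on assumed shares and an assumed gap. The sample size arithmetic is sound.

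The duration inconsistency is real and certain, but it concerns a secondary outcome and adds no weight to the primary point.

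**What to change.** - Make the primary estimate a block difference over all patients, stratified by (or adjusted for) pain instrument.
- State which VAS score, rest or movement, enters it alongside the single PAINAD score.
- Apply the 1.5 margin to this combined stratified estimate.
- Keep the within-VAS and within-PAINAD results as supporting analyses.
- Reconcile the two duration definitions, and say how patients scored on the PAINAD are handled.

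The instrument is already determined for each patient, so the change is to the analysis wording and needs no new data. The cost is a small loss of power if impairment is unbalanced: about 0.78-0.815 against 0.815 under the shares assumed above. Stratifying by instrument removes the artefact described here. It does not deal with other differences between patients given different blocks.
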